Cycle 1:

Ublituximab			Umbralisib	Acalabrutinib
Day 1	Day 2	Day 8 & 15	Daily	Every 12 hours
150 mg	750 mg	900 mg	800 mg	previously tolerated dose

[figure not shown]
Cycles 2 through 6:

Ublituximab	Umbralisib	Acalabrutinib
Day 1	Daily	Every 12 hours
900 mg	800 mg	previously tolerated dose

Cycles 7-24:

Ublituximab	Umbralisib	Acalabrutinib
Day 1 of Cycles 9, 12, 15, 18, 21 and 24	Daily	Every 12 hours
900 mg	800 mg	previously tolerated dose

Study Schema - Re-Treatment

*Progression Of Disease (PD) – Defined per the iwCLL Criteria (Hallek 2018)

U2 – ublituximab and umbralisib; IB – ibrutinib; ACALA – Acalabrutinib; VEN – venetoclax; MRD – minimal residual disease; EOS – end of study

Retreatment will start with 2 cycles of single agent treatment with ibrutinib, acalabrutinib or venetoclax per the subject's history on study. Umbralisib and ublituximab will be started in Cycle 3 of re-treatment. Subjects will again be evaluated with serial peripheral blood MRD analysis. If subjects achieve U-MRD status in the peripheral blood, MRD will again be assessed by peripheral blood 4 weeks later to confirm U-MRD. Retreatment will continue until the occurrence of confirmed U-MRD response in the peripheral blood, completion of 26 cycles (24 cycles of triplet therapy), definitive disease progression, unacceptable toxicity, or withdrawal from the study due to investigator decision or other reasons. Subjects who discontinue study treatment and have not progressed will continue to be followed for disease progression.

Re-treatment schedule as follows:

Cohort A: Ublituximab and Umbralisib with Ibrutinib

Cycles 1 and 2:

Ibrutinib				
Daily				
Daily at previously tolerated dose. Investigator discretion may be used to start subjects at a higher dose than last tolerated (maximum dose 420mg daily).				

Cycle 3:

Ublituximab			Ibrutinib	Umbralisib
Day 1	Day 2	Day 8 & 15	Daily	Daily
150 mg	750 mg	900 mg	At appropriate dose based on initial protocol treatment	Previously tolerated dose. Investigator discretion may be used to start subjects at a higher dose than last tolerated (maximum dose 800mg daily).

Cycles 4 through 8:

Ublituximab	Ibrutinib	Umbralisib
Day 1	Daily	Daily
900mg	At appropriate dose based on previous Cycle	At appropriate dose based on previous Cycle

Cycle 9 through Cycle 26:

Ublituximab	Ibrutinib	Umbralisib
Day 1 of Cycle 11, 14, 17, 20, 23 & 26	Daily	Daily
900 mg	At appropriate dose based on previous Cycle	At appropriate dose based on previous Cycle

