Cohort C: Ublituximab and Umbralisib with Acalabrutinib																				
Cycle 1:																				

  
 Ublituximab	Umbralisib	Acalabrutinib	
 
 Day 1	Day 2	Day 8 & 15	Daily	Every 12 hours	
   
 150 mg	750 mg	900 mg	800 mg	previously tolerated dose	
  
						Ublituximab		Umbralisib	Acalabrutinib		Day 1	Day 2	Day 8 & 15	Daily	Every 12 hours	150 mg	750 mg	900 mg	800 mg	previously tolerated dose
Ublituximab		Umbralisib	Acalabrutinib																	
Day 1	Day 2	Day 8 & 15	Daily	Every 12 hours																
150 mg	750 mg	900 mg	800 mg	previously tolerated dose																
Cycles 2 through 6:																				

  
 Ublituximab	Umbralisib	Acalabrutinib	
   
 Day 1	Daily	Every 12 hours	
 
 900 mg	800 mg	previously tolerated dose	
  
						Ublituximab	Umbralisib	Acalabrutinib	Day 1	Daily	Every 12 hours	900 mg	800 mg	previously tolerated dose						
Ublituximab	Umbralisib	Acalabrutinib																		
Day 1	Daily	Every 12 hours																		
900 mg	800 mg	previously tolerated dose																		
Cycles 7-24:																				

  
 Ublituximab	Umbralisib	Acalabrutinib	
   
 Day 1 of Cycles 9, 12, 15, 18, 21 and 24	Daily	Every 12 hours	
 
 900 mg	800 mg	previously tolerated dose	
  
						Ublituximab	Umbralisib	Acalabrutinib	Day 1 of Cycles 9, 12, 15, 18, 21 and 24	Daily	Every 12 hours	900 mg	800 mg	previously tolerated dose						
Ublituximab	Umbralisib	Acalabrutinib																		
Day 1 of Cycles 9, 12, 15, 18, 21 and 24	Daily	Every 12 hours																		
900 mg	800 mg	previously tolerated dose																		
Study Drugs	Ublituximab is a recombinant chimeric monoclonal antibody against the CD20 antigen, available as a 25 mg/mL concentrate for solution for infusion, supplied by TG Therapeutics, Inc.																			

Umbralisib is a highly specific and orally available dual inhibitor PI3K delta (δ) and CK-1 epsilon available in 200 mg tablets, supplied by TG Therapeutics, Inc.

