5.4 RETREATMENT PHASE

Study Schema for Re-Treatment

*Progression Of Disease (PD) – Defined per the iwCLL Criteria (Hallek 2018)
U2 – ublituximab and umbralisib; IB – ibrutinib; ACALA – Acalabrutinib; VEN – venetoclax; MRD – minimal residual disease; EOS – end of study

Subject on treatment-free observation who subsequently develop clinical progression requiring treatment per iwCLL criteria (Hallek, et al., 2018) after 6 months of treatment-free observation will be retreated with the triple combination regimen that was previously received. Subjects who progress within 6 months of treatment-free observation discontinue from the study.

For subjects enrolled in Cohort A, retreatment will consist of 2 cycles of ibrutinib followed by treatment with ublituximab and umbralisib with ibrutinib cycles 3 through 26 of retreatment. The previously tolerated ibrutinib dose should be considered but is at investigator discretion (maximum dose 420mg daily).

For subjects enrolled in Cohort B, venetoclax should be initiated per the package insert. The target ramp-up dose should be considered based on the previously tolerated dose but is at investigator discretion (maximum dose 400mg daily). Retreatment will consist of 2 cycles of venetoclax followed by treatment with ublituximab and umbralisib with venetoclax cycles 3 through 26.

For subjects enrolled in Cohort C, retreatment will consist of 2 cycles of acalabrutinib followed by treatment with ublituximab and umbralisib and acalabrutinib cycles 3 through 26 of retreatment. The previously tolerated acalabrutinib dose should be considered but is at the investigator discretion.

Clinical response and U-MRD rate will be studied upon retreatment. If subjects achieve U-MRD status in the peripheral blood, MRD will be assessed by peripheral blood 4 weeks later to confirm U-MRD. Retreatment will continue until the occurrence of confirmed U-MRD response in the peripheral blood, completion of 26 cycles (24 cycles of triplet therapy), UTX-TGR-208

Version 2.0 Dated: 30 July 2020

definitive disease progression, unacceptable toxicity, or withdrawal from the study due to investigator decision or other reasons. Subjects who discontinue study treatment and have not progressed will continue to be followed for disease progression.

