7.3 STUDY ASSESSMENT AND TREATMENT SCHEDULE – RE-TREATMENT

Cycle=28 days	Screen	Cycle 1 ¹				Cycle 2 ²		Cycle 3 ³				Cycles 4-8 ⁴		C11-C26 ⁵	EOS ⁶	LTFU
Procedures/Days	D-28 to D1	D1	D8 ⁶	D15 ⁷	D22 ⁷	D1	D8 ⁷	D1	D2	D8	D15	D1	D1 every 3 Cycles			
Physical Examination	X	X				X		X				X	X	X		
ECOG PS	X	X				X		X				X	X	X		
Vital Signs ⁸	X	X	X	X	X	X	X	X	X	X	X	X	X	X		
12-Lead EKG	X															
Hematology	X	X	X	X	X	X	X	X	X	X	X	X	X	X	X	
Chemistry	X	X	X	X	X	X	X	X	X	X	X	X	X	X	X	
Coagulation Studies	X	X				X		X					X	X		
HCV, HBV, CMV ⁹	X															
CMV surveillance ¹⁰								X				C6&8	C11, 14, 17 etc			
MRD-PB ¹¹	X											X ²⁶	X ²⁶			
β ₂ -microglobulin	X															
Pregnancy Test ¹³	X					X		X				X	X			
Response Assessments ¹⁴	X											C7	X ¹⁵		X ¹⁶	
Tumor Lysis Risk Assessment ¹⁷		X														
AE Assessment	X	X	X	X	X	X	X	X	X	X	X	X	X	X	X	
Con Meds	X	X	X	X	X	X	X	X	X	X	X	X	X	X	X	
Ublituximab ¹⁸								X	X	X	X	X	X	X	X	
Umbralisib ¹⁹												Daily until confirmed U-MRD				
Cohort A: Ibrutinib ²⁰												Daily until confirmed U-MRD				
Cohort B: Venetoclax ²¹												Dose ramp-up as per package insert and daily until confirmed U-MRD				
Cohort C: Acalabrutinib												Every 12 hours until confirmed U-MRD				

¹ Treatment Administration +/- 1 day window after cycle 1 day 1. Physical Exam, Vital Signs, ECOG PS, Hematology and Serum Chemistry visit days have - 1 day window. All assessments must be completed prior to treatment.

² Treatment Administration +/- 3 day window. Physical Exam, Vital Signs, ECOG PS, Hematology and Serum Chemistry visit days have a - 3 day window during Cycles 2 through 6.

³ Treatment Administration +/- 7 day window. Physical Exam, Vital Signs, ECOG PS, Hematology and Serum Chemistry visit days have a - 7 day window.

⁴ Treatment Administration +/- 3 day window. Physical Exam, Vital Signs, ECOG PS, Hematology and Serum Chemistry visit days have a - 3 day window during Cycles 2 through 6.

⁵ Day 1 every 3 Cycles (Cycle 11, 14, 17, 20, 23, 26): Treatment Administration +/- 7 day window. Physical Exam, Vital Signs, ECOG PS, Hematology and Serum Chemistry visit days have a - 7 day window.

⁶ Cycle 1 Days 8, 15 & 22 assessments only for subjects receiving venetoclax.

⁷ Cycle 2 Day 8 assessments only for subjects receiving venetoclax.

⁸ Vital signs to include temp, BP, HR, respirations and weight (weight only at baseline).

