⁹ Serum Virology to include HBsAg, HBC antibody, HCV antibody, CMV IgG and CMV IgM or CMV by PCR. If HBC antibody is positive, the subject must be evaluated for the presence of HBV DNA by PCR - See Appendix D. If the subject is CMV IgG or CMV IgM positive, the subject must be evaluated for the presence of CMV DNA by PCR.

¹⁰ CMV surveillance by PCR every 3 cycles while receiving study treatment. In addition, a final CMV test by PCR should be done upon treatment discontinuation if not already done within previous 3 months.

¹¹ For retreatment, MRD analysis should be done within 30 days of restarting therapy in peripheral blood (PB) then performed Cycles 6, 8, 11, 14, 17, 20, 23, and 26. If U-MRD in PB during retreatment repeat approximately 4 weeks later. If U-MRD confirmed approximately 4 weeks later, discontinue treatment and follow for progression and survival for 24 months.

¹³ For women of childbearing potential: Serum pregnancy test within 3 days prior to Cycle 1/Day 1; Urine pregnancy tests on Day 1 of each treatment cycle +/- 7 days.

¹⁴ Radiology assessment should include contrasted CT or MRI imaging of neck, chest, abdomen, and pelvis. Scans to be completed within 30 days prior to Cycle 1/Day 1.

¹⁵ Re-treatment subjects – radiology and response assessment within 14 days of Cycles 7, 14, 20, 26 then every 12 months thereafter. At the time of response assessment, bone marrow to be performed as per standard of care if other criteria for complete remission are met. CR should only be confirmed once by bone marrow assessment at planned response assessments.

¹⁶ Response Assessment to be done as per SOC to determine progression-free survival

¹⁷ For subjects being re-treated with venetoclax only. Refer to section 8.3.5.1

¹⁸ Ublituximab Cycle 3 Days 1,2, 8 & 15; Cycle 4-8 Day 1 then every 3 cycles (C11, C14, C17, C20, C23, C26). No further ublituximab after cycle 26

¹⁹ When starting retreatment, dose of umbralisib is at the investigator's discretion, previously tolerated dose should be considered.

²⁰ When starting retreatment, dose of ibrutinib or acalabrutinib is at the investigator's discretion, previously tolerated dose should be considered.

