Day 1	Day 2	Day 8 & 15	Every 12 hours	Daily

UTX-TGR-208

Version 2.0 Dated: 30 July 2020

150 mg	750 mg	900 mg	At appropriate dose based on initial protocol treatment.	Previously tolerated dose. Investigator discretion may be used to start subjects at a higher dose than last tolerated (maximum dose 800mg daily).
--------	--------	--------	--	---

Cycles 4 through 8:

Ublituximab	Umbralisib	Acalabrutinib
Day 1	Daily	Every 12 hours
900 mg	800 mg	previously tolerated dose

Cycles 9-26:

Ublituximab	Umbralisib	Acalabrutinib
Day 1 of Cycles 11, 14, 17, 20, 23 & 26	Daily	Every 12 hours
900 mg	800 mg	previously tolerated dose

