8.3.2 GUIDELINES FOR ADMINISTRATION OF UMBRALISIB

- *Method of Administration:* Umbralisib will be administered orally once daily at approximately the same time with food
- *Potential Drug Interactions:* No Drug Interactions have been reported to date.
- *Pre-medications:* Subjects are required to start prophylaxis for pneumocystis jiroveci pneumonia (PJP) and antiviral therapy prior to Cycle 1 Day 1 of initial treatment and prior to Cycle 3 Day 1 during retreatment. The following prophylaxis approaches are recommended:
 - *Anti-viral Prophylaxis:* Valtrex 500 mg daily or Acyclovir 400 mg BID or equivalent.
 - *PJP Prophylaxis:* Dapsone 100 mg daily or Atovaquone 1,500 mg once daily or equivalent

Final choice of PJP and anti-viral prophylaxis therapy and schedule is per investigator discretion.

If anti-viral or anti-bacterial prophylaxis is not tolerated, we recommend alternating to a different prophylactic agent, reducing the dose or modifying the schedule for the prophylactic agent, or discontinuing prophylaxis at investigator discretion.

Umbralisib will be dispensed at the sites by the research coordinator or designee under the direction of the PI or by a pharmacist at the site. Subjects must be provided drug in its original container. Subjects should be instructed to return all empty and partially filled bottles with any unused tablets when they return to the site. For the purpose of drug accountability and dosing, subjects should record any missed doses of umbralisib on a drug diary. Study drug compliance should be reviewed with the subject at the beginning of each new treatment cycle and as needed. Missed doses will be documented in the subjects' medical record.

Umbralisib will be self-administered by the subject. Tablets should be taken at approximately the same time each day with food. Subjects should be instructed to swallow the tablets whole and should not chew or crush them.

If a dose of umbralisib is missed, it should be taken as soon as possible on the same day. If it is missed for a period greater than 12 hours, it should not be replaced. If vomiting occurs, no attempt should be made to replace the vomited dose.

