8.4.2 DOSE DELAY/MODIFICATIONS: UMBRALISIB

Supportive care should be considered for any subject who experiences Grade ≥ 2 cytopenias, or Grade ≥ 1 non-hematologic toxicities.

If a subject discontinues one study drug, the subject may continue treatment with the other study drug(s) per the protocol.

TABLE 3: UMBRALISIB DOSE DELAY AND/OR MODIFICATIONS GUIDANCE

NCI-CTCAE Grade	Dose Delay and/or Modification
Hematologic Adverse Event	
Neutropenia	
Grade \leq 2 neutropenia	Maintain current dose. Consider supportive care as warranted.
Grade 3 neutropenia	Maintain current dose, consider supportive care. If recurrence or persistent Grade 3, consider reducing umbralisib to next lower dose level or maintain current umbralisib dose at discretion of the investigator.
Grade 4 neutropenia or occurrence of neutropenic fever or infection	Delay umbralisib until Grade \leq 3 and/or neutropenic fever or infection is resolved; thereafter, resume at full dose. Consider supportive care. If recurrence after re-challenge, delay umbralisib until Grade \leq 3 and/or neutropenic fever or infection is resolved; thereafter, resume umbralisib at current dose or at next lower dose level at discretion of the investigator.
Thrombocytopenia	
Grade \leq 3 thrombocytopenia	Maintain current dose level and provide supportive care as clinically warranted.
Grade 4 thrombocytopenia	Delay umbralisib until Grade \leq 3; thereafter, resume at full dose. Consider supportive care intervention as warranted. If recurrence after re-challenge, delay umbralisib until Grade \leq 3; thereafter resume umbralisib at current dose or at next lower dose level at discretion of the investigator.
Pulmonary & Related Infections*	
Grade 1 & 2	Stop all therapy and hold until complete resolution. Restart umbralisib at one lower dose level. Restart ublituximab (if applicable) at full dose. If recurrence after re-challenge, discontinue all treatment therapy.
Grade \geq 3	Discontinue all therapy
For sinopulmonary infections clearly not related to immune-mediated pneumonitis, umbralisib may be continued at investigator's discretion. While pneumonitis has been minimal with umbralisib, it is a reported adverse event associated with other PI3K delta inhibitors. Use of anti-pneumocystis and anti-herpetic viral prophylaxis is required for subjects receiving umbralisib.	
Diarrhea and/or Colitis	

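### Two Cohort C re-treatment dosing tables are internally inconsistent: the Synopsis table starts the triplet in Cycle 1 instead of Cycle 3, and the 8.2 table prints a flat umbralisib 800 mg from Cycle 4

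*Combined protocol and SAP*

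**What the plan says.** **Sequence.** For the acalabrutinib cohort, section 5.4 states that "retreatment will consist of 2 cycles of acalabrutinib followed by treatment with ublituximab and umbralisib and acalabrutinib cycles 3 through 26 of retreatment", with 26 cycles in total, 24 of them triplet. The Synopsis text that introduces the re-treatment tables says the same for all cohorts: "Umbralisib and ublituximab will be started in Cycle 3 of re-treatment". Footnote 18 of 7.3 schedules "Ublituximab Cycle 3 Days 1,2, 8 & 15; Cycle 4-8 Day 1 then every 3 cycles". The 8.2 Cohort C table starts ublituximab and umbralisib in Cycle 3, and the interrupted-infusion rule (8.3.1.1), flow rates (8.3.1.2) and dilutions (8.3.1.3.1) all place the first re-treatment infusions in Cycle 3.

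**The table that differs.** The Synopsis Cohort C re-treatment table follows the Cohort A and B re-treatment tables, but lists ublituximab on Days 1, 2, 8 and 15 and umbralisib 800 mg in Cycle 1. It continues through Cycles 2-6 and places later ublituximab on "Day 1 of Cycles 9, 12, 15, 18, 21 and 24". Those are the cycles of the initial-treatment tables.

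**Umbralisib dose.** In 8.2, all three cohorts start Cycle 3 at the previously tolerated umbralisib dose, with discretion to go higher up to 800 mg. From Cycle 4, Cohorts A and B carry forward the dose of the preceding cycle. Cohort C prints 800 mg for Cycles 4-8 and again for Cycles 9-26.

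**The concern.** These are operative dosing tables, the part of a protocol that a site or pharmacy is most likely to work from. A site using the Synopsis table would start ublituximab and umbralisib two cycles early, with no acalabrutinib lead-in. The supporting procedures are timed to Cycle 3. Footnote 6 of 7.3 reads "Cycle 1 Days 8, 15 & 22 assessments only for subjects receiving venetoclax", and the 7.3 grid has no Cycle 1 Day 2 visit. Section 8.3.2 times the start of pneumocystis and antiviral prophylaxis as "prior to Cycle 1 Day 1 of initial treatment and prior to Cycle 3 Day 1 during retreatment".

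A site reading the 8.2 table literally would raise a subject restarted at 600 mg or 400 mg to 800 mg at Cycle 4.

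Response, complete response, U-MRD rate and PFS on re-treatment are secondary objectives (3.1). If some subjects followed one schedule and some the other, the same nominal cycle would mean different triplet exposure.

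**Working it through.** **1. The plan's own count (5.4).** Triplet Cycles 3 to 26: 26 − 3 + 1 = 24. Adding 2 single-agent cycles gives 26. Section 5.4 is consistent with itself.

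**2. The two Cohort C schedules side by side.**

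| | 5.4, 7.3 footnote 18, 8.2 | Synopsis Cohort C table |
|---|---|---|
| Cycles 1-2 | acalabrutinib alone | full triplet |
| Split first ublituximab dose | Cycle 3 | Cycle 1 |
| Day 1 ublituximab, consecutive cycles | 4-8 | 2-6 |
| Later ublituximab | 11, 14, 17, 20, 23, 26 | 9, 12, 15, 18, 21, 24 |
| Umbralisib at start | previously tolerated dose, maximum 800 mg (8.2) | 800 mg |
| Last cycle | 26 | 24 |

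The two lists of later ublituximab cycles have no cycle in common.

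**3. Exposure in re-treatment Cycles 1-2 under the Synopsis table.**
- Ublituximab, Cycle 1: 150 + 750 + 900 + 900 = 2,700 mg (4 infusions). Cycle 2 Day 1: 900 mg (1 infusion). Sum: 3,600 mg in 5 infusions, against 0.
- Umbralisib: 2 × 28 = 56 days at most, against 0.
- Infusions without a scheduled Cohort C assessment in 7.3: Cycle 1 Day 2 (no such visit) and Days 8 and 15 (venetoclax subjects only), so 3 of the 5.

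**4. Cumulative ublituximab.**
- Synopsis table: 2,700 + 5 × 900 + 6 × 900 = 12,600 mg; 4 + 5 + 6 = 15 infusions.
- 8.2 table: 2,700 + 5 × 900 + 6 × 900 = 12,600 mg; 15 infusions.

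**5. Timing of the first on-treatment MRD sample.** Footnote 11 of 7.3 puts it in re-treatment Cycle 6. Under 8.2 that is triplet cycle 6 − 2 = 4; under the Synopsis table it is triplet cycle 6.

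**6. The flat umbralisib dose in 8.2, read literally.** Cycles 4 to 26 are 23 of the 24 triplet cycles (23 × 28 = 644 days). For a subject restarted at 600 mg the rise is 200 mg/day (800/600 = 1.33, or 33%); at 400 mg it is 400 mg/day (800/400 = 2, or 100%). For a subject restarted at 800 mg it is zero. It is also zero wherever the 8.4.2 bar on re-escalation after a reduction for study-drug-related toxicity is applied.

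**The case against.** **A careful site would notice.** Every other statement of the re-treatment sequence says Cycle 3, including the Synopsis text above the tables, and section 6 requires a re-treatment registration form to be sent to the sponsor. This stands as mitigation. It does not make the table right, and safe dosing should not depend on staff spotting the contradiction.

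**Missed prophylaxis.** A reader might infer that umbralisib would be given unprotected in Cycles 1-2. The documents do not go that far: 8.4.2 says "Use of anti-pneumocystis and anti-herpetic viral prophylaxis is required for subjects receiving umbralisib", and exclusion criterion 4 has the same requirement, whatever the cycle. Only the timing sentence in 8.3.2 would be out of step.

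**The 800 mg is only nominal.** The 8.1 tables print 800 mg for every cycle, and Table 4 calls it the starting dose; nobody reads 8.1 as cancelling dose reductions. Footnote 19 of 7.3 also leaves the umbralisib dose at the start of re-treatment to the investigator, with regard to the dose tolerated before. This largely stands, and it is why the 8.2 point is the lesser one. What remains is that the flat dose follows an individualised dose within the same course and differs from the other two cohorts, with no reason given.

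**A wider conflict with 8.4.** A reader might infer that the Cycle 3 discretion to exceed the last tolerated dose, and the unqualified return to the triplet, breach the dose-modification rules, so that re-treatment needs a stricter rule. The documents do not support that. Section 8.4 is general and applies to re-treatment without a cross-reference. The discretion is printed for all three cohorts in 8.2, capped at 800 mg, and used only after more than 6 months off treatment, so it may well be deliberate. Narrowing it would be a new dosing rule, not a correction.

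**Conclusion.** Both inconsistencies hold and should be corrected. They are errors of drafting, not choices of design.

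The Synopsis Cohort C re-treatment table is wrong as written. If followed, it brings 5 infusions (3,600 mg) of ublituximab and up to 56 days of umbralisib into two cycles meant for acalabrutinib alone, with 3 infusions on days without a scheduled assessment. It should not be read as an overdose, because total ublituximab is identical. The 8.2 entry is a wording error whose effect disappears if 8.4.2 is followed.

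The consequences are confined to re-treated Cohort C subjects and the secondary re-treatment endpoints. The primary U-MRD rate, which comes from initial treatment, is untouched. The number affected cannot be derived from the documents. Cohort C is capped at about 28 subjects, only those who progress after 6 months of observation and need treatment are re-treated, and the number may be zero. The exposure figures assume that a site follows the table literally and that no dose is delayed or missed.

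**What to change.** 1. In the 8.2 Cohort C table, replace the umbralisib 800 mg entries for Cycles 4-8 and Cycles 9-26 with the Cohort A and B wording, which carries the dose forward from the previous cycle.
2. Replace the Synopsis Cohort C re-treatment table with the corrected 8.2 table: acalabrutinib alone in Cycles 1-2; split-dose ublituximab plus umbralisib at the previously tolerated dose (maximum 800 mg) from Cycle 3; ublituximab on Day 1 of Cycles 4-8, 11, 14, 17, 20, 23 and 26. This gives 15 infusions, 24 triplet cycles and 26 cycles in total, in line with 5.4.

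The cost is two table corrections in the next amendment, with no new visits, data or subjects. Until then, a short note to sites with Cohort C subjects in observation would cover the gap.
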